Currently, procalcitonin concentration is measured in all surgical ICU patients for whom a BAL is sent on the day of the BAL as part of a separate non-interventional study. For the purposes of the current trial, procalcitonin concentration will also be measured during treatment in order to assess response, as well as following treatment in order to assess for recurrence. Because study entry will occur at the time that VAP is confirmed microbiologically (approximately 72 hours following the BAL and initiation of empiric antibiotics), these measurements will begin after three days of antibiotic therapy. Procalcitonin concentration will then be measured daily for the remainder of treatment, as well as daily for 72 hours following treatment. Thus, the 4 day group will have procalcitonin concentration measured at baseline, treatment days 3 and 4, and post treatment days 1-3. The 8 day group will have procalcitonin measured at baseline, treatment days 3-8, and post-treatment days 1-3. The treatment team will have access to the results of these measurements. For the purposes of the trial, biomarker resolution will be defined as a procalcitonin concentration $< 0.5 \mu\text{g/L}$ or a decrease of $\geq 80\%$ relative to the day of the BAL [26].

Additional Outcomes: Days of antibiotics, antibiotic days (defined as the product of days of antibiotics and number of antibiotics per day), recurrence, ventilator days, empyema, need for tracheostomy, non-pulmonary infections, ICU length of stay (LOS), hospital LOS, and mortality. Recurrence is defined using the same clinical and microbiologic criteria as the initial episode of VAP, and occurring 2-14 days

following completion of initial therapy. Relapse is defined as recurrent VAP caused by the initial pathogen; super-infection is defined as recurrent VAP caused by ≥ 1 new pathogen. VAP occurring > 14 days following completion of initial therapy will be considered a second episode of pneumonia as opposed to a recurrence. The incidence of recurrent VAP due to a MDR pathogen, as well as any other infection caused by a MDR pathogen, will also be abstracted.

Baseline Variables: Age (years), gender, admission diagnosis, associated diagnoses, admission APACHE II score, comorbidity index [27], prior and current antibiotic exposure, base deficit, serum lactate concentration, time from ICU admission to BAL, presence of organisms on gram stain, and presence of polymorphonuclear lymphocytes on gram stain.

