Sample acquisition and processing: The default method for BAL specimen acquisition will be via the blind or “mini” BAL technique [18], using an 85 mm by 4 mm bronchial diagnostic catheter (Combicath, ® Prodimed, Neuilly-en-Thelle, France). The catheter is passed through the artificial airway until resistance is met. It is then withdrawn approximately 1 cm and the inner lavage catheter is deployed. Lavage is then performed with 20 – 40 mL of sterile saline.

The BAL will be obtained bronchoscopically if bronchoscopy is being performed for another indication (e.g., pulmonary toilet, percutaneous dilational tracheostomy). Lavage is performed using 20-40 mL of normal saline lavage into the lobar bronchus that appears most abnormal on CXR.

Using a 0.001 calibrated loop, vortexed BAL specimens will be plated onto sheep blood, MacConkey, and Chocolate agar at 35°C - 37°C in CO₂. Plates will be examined after 24, 48, and 72 hours prior to issuing a final negative report. 100 or more colonies per plate is considered significant and represents $\geq 10^5$ cfu/mL.

Statistical Analyses:

Power analysis: Power analysis was performed using SAS Version 9.1 (SAS, Inc., Carey, NC, *proc power*). The Analysis was based on a non-inferiority study design, defined as a difference in outcomes between the 4 day and 8 day groups of < 10%. Furthermore, as the intention was to show non-inferiority, tests were one-sided using an alpha error level of 0.10. The beta error level was set at 0.20 for 80% power. Analysis for the outcome of VAP recurrence returned the largest sample size. From 2010-2012, during which time VAP was treated with ≥ 8 days of therapy, the incidence of recurrent VAP in the DHMC surgical ICU was approximately 25%. Projecting a recurrence rate after 4 days of treatment of 35% returns a total sample size of 103..

Interim Analysis: An interim analysis will be conducted for all outcomes after 50% accrual (n_{total}=50).

Data Analysis: Data analyses will be performed using SAS Version 9.1 (SAS, Inc., Carey, NC). Data will be analyzed using an intention-to-treat strategy (i.e., patients randomized to receive 4 days of antibiotic therapy will be analyzed with this group even if they receive longer courses). Data will be expressed as median (range) or number (%). Normality of continuous variables will be assessed using the

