Kolmogorov-Smirnov test. Differences in the means of continuous variables that are distributed normally will be assessed using the Student's t-test. Differences in the medians of continuous variables that are not distributed normally will be assessed using the Wilcoxon Rank Test. Proportions of categorical variables will be compared using the chi-squared test. When expected cell counts are < 5, Fischer's exact test will be used. Univariate analysis of categorical outcomes will be expressed as the relative risk with 95% confidence intervals. A logistic regression model will be fit to address possible confounding by differences in baseline parameters between groups. Baseline variables associated with randomization status at the $p<0.25$ level by univariate analysis will be added to the model using a forward selection method. The overall contribution of the fitted model to predicting variability in the outcome of interest will be assessed using the likelihood ratio chi-squared test. The independent contribution of individual variables will be assessed using the Wald chi-squared test. Model fit was will be assessed using the Hosmer-Lemeshow goodness-of-fit chi-squared statistic, with $p>0.05$ indicating acceptable model calibration. The alpha error level is defined at 0.05, with statistical significance set at $p<0.05$.

Adverse Event Monitoring and Reporting: Adverse event monitoring will occur daily. The safety of the study will be monitored by an independent, external Data Safety Monitoring Board, consisting of a medical intensivist, and an infectious disease physician. The committee will meet biannually and submit written reports to the IRB.

References:

1. Edwards, J.R., K.D. Peterson, Y. Mu, S. Banerjee, K. Allen-Bridson, G. Morrell, et al., National Healthcare Safety Network (NHSN) report: data summary for 2006 through 2008, issued December 2009. *Am J Infect Control* 2009;37:783-805
2. Neu, H.C., The crisis in antibiotic resistance. *Science* 1992;257:1064-73
3. Mahgoub, S., J. Ahmed, and A.E. Glatt, Completely resistant *Acinetobacter baumannii* strains. *Infect Control Hosp Epidemiol* 2002;23:477-9
4. Kollef, M.H. and V.J. Fraser, Antibiotic resistance in the intensive care unit. *Ann Intern Med* 2001;134:298-314
5. Bradley, J.S., R. Guidos, S. Baragona, J.G. Bartlett, E. Rubinstein, G.G. Zhanel, et al., Anti-infective research and development--problems, challenges, and solutions. *Lancet Infect Dis* 2007;7:68-78

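### Daily procalcitonin has only a yes/no, undated resolution endpoint; a baseline-adjusted analysis of log procalcitonin over treatment days 5-7 would use the data far better at no extra sampling

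*Combined protocol and SAP*

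**What the plan says.** The Outcomes section divides effectiveness into clinical, microbiologic and biomarker response.

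Under Biomarker Response, the one defined endpoint is a flag: "biomarker resolution will be defined as a procalcitonin concentration" under 0.5 µg/L, or a drop of 80% or more relative to the BAL day. The day on which it is judged is not given.

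The sampling schedule differs by arm. For the short arm: "Thus, the 4 day group will have procalcitonin concentration measured at baseline, treatment days 3 and 4, and post treatment days 1-3". For the long arm, baseline followed by "treatment days 3-8, and post-treatment days 1-3".

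Study Flow & Stop Criteria places randomisation on the morning after the fourth day of appropriate antibiotics.

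Data Analysis offers, for continuous outcomes, only two-sample comparisons: "Differences in the means of continuous variables that are distributed normally will be assessed using the Student's t-test", with a Wilcoxon test otherwise. Proportions get a chi-squared or exact test, and the only adjusted model is logistic regression. "The alpha error level is defined at 0.05, with statistical significance set at" p<0.05.

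CPIS is scored at baseline and daily, without a response cut-off, comparison day or summary measure.

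**The concern.** The trial collects five post-baseline procalcitonin values per patient in one arm and nine in the other, then defines an endpoint that records only whether a threshold was crossed. It does not use how far procalcitonin fell or how several days agree. The BAL-day value enters only through the 80% criterion.

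Two things are at stake. First, the hypothesis is that 4 days is as effective as 8. Where the analysis consists of difference tests at p<0.05, an insensitive comparison makes a finding of no difference more likely, and that finding may be read as support for the hypothesis. Second, because no day is named, the flag could be read as resolved at any scheduled measurement. That would give the 8-day arm more opportunities to resolve than the 4-day arm, which is a bias as well as a loss of precision.

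**Working it through.** The plan gives no figure for information loss, resolution rate, standard deviation or within-patient correlation. Its sample size of 103 was set on VAP recurrence and does not depend on this endpoint. Everything numerical below, apart from the day counts, therefore rests on stated assumptions.

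**1. Which days can be compared.** From the Biomarker Response schedule and the time of randomisation:

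- 4-day arm: days 3 and 4, then post-treatment days 1-3, which are days 5, 6 and 7. That is 2 + 3 = 5 values, 3 of them after randomisation.
- 8-day arm: days 3-8, then post-treatment days 1-3, which are days 9, 10 and 11. That is 6 + 3 = 9 values, 7 of them after randomisation.
- Days shared after randomisation: 5, 6 and 7. No planned analysis names them.
- An 'ever resolved' reading gives 5 against 9 chances, or 3 against 7 counting only post-randomisation values.

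**2. Benchmark: one normal value cut at a fixed point.** Relative efficiency = φ(z)² / [p(1−p)], where p is the proportion resolved and z its normal quantile.

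| p | φ(z) | Efficiency | Loss |
|---|---|---|---|
| 0.5 | 0.399 | 0.637 | 36% |
| 0.6 | 0.386 | 0.622 | 38% |
| 0.7 | 0.348 | 0.576 | 42% |
| 0.8 | 0.280 | 0.490 | 51% |
| 0.9 | 0.175 | 0.342 | 66% |

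The minimum loss is 36%, at an even split.

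**3. The actual flag.** It is met when log procalcitonin is below the larger of log 0.5 and (BAL-day log value + log 0.2). Its threshold therefore moves with baseline, and the benchmark formula does not describe it. Its efficiency against a continuous comparator is (dp/dδ)² / [p(1−p)] × V, where δ is a shift in mean log procalcitonin and V is the comparator's variance.

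Assumptions: BAL-day log SD 1.2, slope on baseline 0.6, residual SD s of 0.6-1.0, and residual correlation between days 0.6.

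- Variance explained by baseline: 0.6² × 1.2² = 0.518.
- Unadjusted one-day variance: 0.518 + s² = 0.878 (s = 0.6) to 1.518 (s = 1.0). Adjustment removes 0.518/0.878 = 59% to 0.518/1.518 = 34% of it.
- Adjusted three-day mean: s² × (1 + 2 × 0.6)/3 = 0.733 s².

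Results for the flag judged on one day:

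- Against an unadjusted same-day test: from a 45% loss to a 27% gain (resolution rates 11-86%).
- Against an unadjusted day 5-7 mean: it keeps about 0.5-1.1 of the information.
- Against a baseline-adjusted same-day value: a 41-77% loss, so it keeps 0.23-0.59.
- Against a baseline-adjusted day 5-7 mean: 0.23 × 0.733 = 0.17 to 0.59 × 0.733 = 0.43. It keeps roughly 0.2-0.4, a loss of about 60-80%.

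One worked point, with assumed medians of 2 µg/L on the BAL day and 0.6 µg/L later and s = 0.8: 58% resolve, and the flag has efficiency 0.92 against the unadjusted one-day test (V = 0.518 + 0.64 = 1.158). The adjusted three-day mean has V = 0.64 × 0.733 = 0.469. So the flag keeps 0.92 × 0.469/1.158 = 0.37, a 63% loss.

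**4. CPIS.** The score is not dichotomised, so none of the above applies to it. Taking one day instead of the mean of three loses 1 − (1 + 2ρ)/3, which is 47% at ρ = 0.3 and 7% at ρ = 0.9. The plan does not say that one day will be used.

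**The case against.** The strongest reply is that the plan does not confine procalcitonin to the flag. The generic continuous-variable tests could be applied to concentrations, and Outcomes plans a sub-analysis relating procalcitonin to clinical and microbiologic response. The flag already uses the BAL-day value through its 80% criterion, and against the unadjusted tests the plan lists it may lose nothing. This stands, and it is why the recommendation depends on baseline adjustment and not simply on analysing a continuous value. It does not remove the gap: no between-arm comparison of concentrations, no common day and no adjusted continuous model is specified.

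A second reply is that days 5-7 ask a different question. By default assignment, the 4-day arm is then off antibiotics and the 8-day arm still on them, whereas microbiologic response is anchored to the day after treatment ends in each arm. This is a real limitation and should be stated, but these are the only post-randomisation days on which the schedule gives procalcitonin in both arms.

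A third reply is that a ratio of means cannot serve a non-inferiority claim. That is correct: the margin is "defined as a difference in outcomes between the 4 day and 8 day groups of < 10"%, and nothing equivalent is set for a concentration ratio.

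Three stronger readings are tempting, and the documents do not support them:

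- A reader might infer that 40% or more of the information is lost in two of the three effectiveness measures. Forty per cent is not a lower bound even for a simple cut, and it cannot be carried over to CPIS.
- A reader might multiply 103 by the benchmark efficiencies and call the result the effective sample size. That formula does not fit a two-part flag that uses baseline.
- A reader might infer that CPIS will be tested separately on every day up to day 28, with an inflated false-positive rate. The plan does not say so, and follow-up ends at discharge if that comes first.

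**Conclusion.** The point holds for procalcitonin. The only defined biomarker endpoint is an undated binary flag, and no repeated-measures or baseline-adjusted continuous analysis is planned, although both arms share three post-randomisation measurement days. The 60-80% loss against the baseline-adjusted day 5-7 mean is conditional on the assumed log-normal spread, baseline slope and residual correlation, and the sponsor's own procalcitonin data should replace these. The difference in measurement opportunities between arms follows from the schedule alone and needs no assumption.

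The sample size is unaffected. For CPIS, the documents support only the narrower statement that no day, cut-off or summary is named.

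**What to change.** - Keep the resolution flag as a reported clinical summary, and judge it on one named post-randomisation day common to both arms.
- Pre-specify, as the between-arm biomarker comparison, the ratio of geometric mean procalcitonin over treatment days 5-7. Estimate it from a mixed model on log procalcitonin with BAL-day log procalcitonin as a covariate, and report a 95% CI.
- Describe this as a supportive estimate and not as a non-inferiority test, since no margin is set on this scale.
- State its limits: approximate log-normality, data missing at random after discharge, and a window in which the default assignments leave one arm off antibiotics and the other on.
- As a secondary suggestion, analyse CPIS with a baseline-adjusted repeated-measures model on the untransformed 0-10 score, over all post-randomisation days commonly observed in both arms. Log values are unsuitable because the score can be 0. Restriction to days 5-7 is unnecessary because CPIS is collected daily in both arms.

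The cost is analysis-plan wording and modest extra programming. No new samples or visits are needed.

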One subset of patients for whom a decreased duration of antimicrobial therapy may be particularly effective is those who develop VAP \leq 7 days after intubation (early VAP). Early VAP comprises the majority of cases of pneumonia diagnosed in the ICU[14] . Furthermore, as compared to patients who develop late VAP, patients who develop early VAP are more likely to be infected with community-acquired pathogens sensitive to narrow spectrum antibiotics [14]. Finally, nearly all cases of

early VAP caused by sensitive pathogens demonstrate MR after relatively short (3-5 days) courses of therapy [10].

The hypothesis of this randomized clinical trial (RCT) is that 4 days of antibiotic therapy, as compared to 8 days, is equally effective and results in decreased antibiotic exposure among surgical ICU patients with early VAP.

Methods:

Study Design: Randomized, double-blind (until treatment day 5) clinical trial.

Intervention: Default 4 vs. 8 days of antibiotic therapy.

Screening Pool: Trauma-Surgical ICUs.

Inclusion Criteria:

- 1) Surgical patient
- 2) Early VAP, defined as:
 - a. Duration of Intubation: 2-7 days [9] (via endotracheal or tracheostomy tube).

- b. Clinical suspicion of pneumonia: New or progressing infiltrate on chest radiograph (CXR) along with ≥ 1 of the following: Temperature $\geq 38.5^{\circ}\text{C}$ or $< 36.5^{\circ}\text{C}$; blood leukocytes $>11,000 \text{ mm}^3$ or $<4,000 \text{ mm}^3$; purulent tracheal secretions; or $\text{PaO}_2:\text{FiO}_2 < 200$ [15].
- c. Quantitative microbiologic confirmation: Bronchoalveolar lavage (BAL) culture showing $\geq 10^5 \text{ cfu/mL}$ of at least one pathogen [16]. The quantitative microbiology threshold will be lowered to $\geq 10^4 \text{ cfu/mL}$ if the patient was being treated with antibiotics to which the pathogen is sensitive at the time of the BAL.

3) Hospital LOS ≤ 10 days at the time that the BAL was obtained.

Exclusion Criteria:

- 1) Age < 18 years.
- 2) Prior episode of VAP for the index admission (the patient may have had prior BALs sent for culture, but these cannot have met the above mentioned diagnostic criteria for VAP).

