The CPIS_{clinical} will be calculated at baseline and daily thereafter during the study period. In the case that certain individual variables are not available for abstraction, they will be left blank rather than obtained solely for the purpose of the study. The worst values (those associated with the highest number of points) for each variable over the 24 hours prior to the BAL will be used. Tracheal secretions will be scored based on daily progress notes from the respiratory therapist. Chest radiograph findings will be scored based on attending final radiologist reads.

It is important to note that CPIS_{clinical} possesses limited accuracy for monitoring VAP resolution in surgical ICU patients [20, 21]. Furthermore, a multicenter RCT reported decreased organ failure, mortality, and antibiotic use for patients with suspected VAP managed using a microbiologic endpoint as compared to a clinical one [22]. For these reasons, efficacy of treatment will also be assessed both microbiologically and using a biomarker of infection (*see below*).

Microbiologic Response: The definition of microbiologic response for VAP reported most commonly ranges from $<10^2$ cfu/mL [23] to $<10^3$ cfu/mL [10] from a repeat BAL culture obtained the day after the end of therapy. For the purposes of this trial, microbiologic response will be defined as growth of the original pathogen of $<10^3$ cfu/mL from a BAL culture obtained the day after the end of treatment. Repeat BALs will thus be obtained on day 5 for the 4-days of antibiotics group and day 9 for the 8 days of antibiotics group. If the patient is no longer intubated at this time, a repeat BAL will not be obtained and MR will be inferred. The treatment team will have access to the results of the repeat BAL.

Biomarker Response: Circulating levels of calcitonin precursors, including procalcitonin, are elevated in bacterial infections [24, 25]. Normalization of procalcitonin concentration in patients receiving therapy for VAP has been shown to both correlate with clinical response and guide discontinuation of antibiotics [26]. The relationship between clinical response, MR, and procalcitonin concentration has not been evaluated prospectively in critically ill patients being treated for VAP and will be the focus of a sub-analysis.

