Study Flow & Stop Criteria: The trial will be reported in accordance with the recommendations of the CONSORT Statement [28]. IRB approval will be obtained. All subjects or their legally authorized representative will provide written consent for study participation. The trial is registered with the US National Institutes of Health (ClinicalTrials.gov Identifier NCT01994980).

Screening will occur daily by study personnel. Eligible patients will be approached as soon as possible after inclusion criteria are met (i.e., 1-3 days prior to randomization). Randomization will occur using a computer-generated block pattern on the morning following the fourth day of appropriate antibiotic therapy.

Empiric antibiotic therapy will be instituted as soon as possible following BAL acquisition. The default antibiotic will be ceftriaxone 2 gram IV q24 hours. Patients with potential allergies to cephalosporins will receive levofloxacin 750 mg IV q24hours. Pre-existing treatment for a non-

pulmonary infection with at least one antibiotic that has appropriate activity against the VAP pathogen may be substituted for the default antibiotic. Once sensitivity data become available (approximately 72 hours after BAL acquisition), therapy may be de-escalated to a more narrow-spectrum agent (e.g., cefazolin) as indicated.

The default duration of antibiotic therapy will be determined by study group assignment; the treatment team will be asked to adhere to study group assignment whenever possible. However, the treatment team may choose to extend the duration of antibiotic therapy based on clinical circumstances, such as deterioration in hemodynamic or respiratory status that is believed to be related to incompletely treated VAP, or continued treatment of a non-pulmonary infection. The treatment team may also decide to extend the duration of antibiotic therapy based on the results of serial procalcitonin measurements. Finally, the treatment team may decide to extend the duration of antibiotic therapy based on the results of the BAL obtained the day after completion of therapy. These clinical decisions will take precedence over study group assignment.

Patients will be followed for 28 days or until hospital discharge, whichever occurs first. Please see attached data collection tool for detailed information.

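### Procalcitonin resolution can be met before randomisation, and the day-4 procalcitonin and CPIS values are not named as baseline covariates

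*Combined protocol and SAP*

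**What the plan says.** **Timing.** Under Study Flow & Stop Criteria, "Empiric antibiotic therapy will be instituted as soon as possible following BAL acquisition", and patients are randomised "on the morning following the fourth day of appropriate antibiotic therapy". The two arms therefore share about four days of treatment after the BAL.

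**Procalcitonin.** Under Biomarker Response, "biomarker resolution will be defined as a procalcitonin concentration" below 0.5 µg/L, or a fall of at least 80% "relative to the day of the BAL". No day is named for reading this rule, and nothing says that resolution must persist. Apart from the BAL-day sample, "these measurements will begin after three days of antibiotic therapy".

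**CPIS.** Under Clinical Response, CPIS_clinical "will be calculated at baseline and daily thereafter during the study period". The only scoring window given is the worst values "for each variable over the 24 hours prior to the BAL will be used". There is no response threshold, change score or time point.

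**Adjustment.** The Baseline Variables list contains neither procalcitonin nor CPIS_clinical. Under Data Analysis, baseline variables become candidates for the logistic model only if they are associated with assignment at p<0.25.

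**The concern.** The trial asks what happens after day 4 when antibiotics stop rather than continue. Biomarker response is one of three ways in which effectiveness, a main outcome, is judged. As written, its definition does not separate resolution reached during shared treatment from status after the arms diverge.

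The protocol gives reason to expect some early response. The Background says that nearly all cases of "early VAP caused by sensitive pathogens demonstrate MR after relatively short (3-5 days) courses of therapy", and Clinical Response expects a good clinical response by day 3. Neither is a procalcitonin figure, but together they make early resolution plausible.

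The values that would describe each patient at randomisation are already collected. The plan does not name them as baseline values and gives them no place in the adjusted comparison.

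**Working it through.** **1. Timeline.** There is no documented resolution rate to reproduce. The sample size of 103 rests on recurrence. It is taken below as stated, for illustration only; whether it follows from its inputs is a separate question. From Biomarker Response and Study Flow & Stop Criteria, scheduled procalcitonin samples by treatment day are:

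| | Before randomisation | After day 4 |
|---|---|---|
| 4-day arm | BAL day, 3, 4 | 5, 6, 7 (post-treatment days 1-3) |
| 8-day arm | BAL day, 3, 4 | 5-8, then 9-11 (post-treatment days 1-3) |

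Two on-treatment samples per patient precede allocation. Afterwards the 4-day arm has 3 scheduled values and the 8-day arm has 7. Days 5, 6 and 7 are common to both. Either limb of the resolution rule can be satisfied on day 3 or 4.

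**2. Dilution if early resolution is credited.** Let q be the share resolved by day 4 and counted as successes, and let s8 and s4 be the later resolution rates among the rest, with d = s8 − s4. Then

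p8 − p4 = [q + (1−q)s8] − [q + (1−q)s4] = (1−q)d.

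The documents give neither q nor d; both are assumed. With d = 20 points:

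| q | Overall difference (1−q)d | Gap among the unresolved that matches a 10-point margin, 10/(1−q) | Unresolved among 103 |
|---|---|---|---|
| 30% | 14 | 14 | about 72 |
| 50% | 10 | 20 | about 52 |
| 70% | 6 | 33 | about 31 |

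**3. Effect on a non-inferiority conclusion.** Take the Power analysis values (margin 10 points, one-sided alpha 0.10, N = 103), 1:1 allocation (assumed, 51.5 per arm), and s8 = 80%, s4 = 60% (assumed). The chance of declaring non-inferiority is Φ[(0.10 − Δ)/SE − 1.28], where Δ = p8 − p4 and SE² = [p8(1−p8) + p4(1−p4)]/51.5.

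| q | p8, p4 | Δ | SE | Chance |
|---|---|---|---|---|
| 0 | 0.80, 0.60 | 0.20 | 0.088 | 0.8% |
| 30% | 0.86, 0.72 | 0.14 | 0.079 | 3.7% |
| 50% | 0.90, 0.80 | 0.10 | 0.070 | 10% |
| 70% | 0.94, 0.88 | 0.06 | 0.056 | 28% |

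**4. When dilution is also error.** Let r4 and r8 be the shares of early resolvers who have rebounded by a common later day. The difference on that day is (1−q)d + q(r4 − r8). Crediting early status removes the second term. If nobody rebounds, that term is zero and (1−q)d is the correct intention-to-treat difference.

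**5. Covariates.** Day-4 procalcitonin is scheduled in both arms, and CPIS_clinical is daily. Because neither is on the Baseline Variables list, the p<0.25 screen has no day-4 value to select, however well it predicts outcome.

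**The case against.** Much of the opposing case stands, and it limits what can be claimed.

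- **CPIS.** A reader might infer that CPIS response is also measured from the BAL. No CPIS response is defined, so the BAL window shows only how baseline is scored. For CPIS the point is confined to the missing covariate.
- **Permanent credit.** A reader might infer that early resolvers count as successes for good and that rebounds go unseen. The protocol does not say so. Procalcitonin is also measured for three days after treatment to look for recurrence, and recurrence at 2-14 days after therapy is a separate outcome. If resolution were read at a fixed later time, a rebound would count as failure. The plan names no such time.
- **Direction.** Randomisation balances early resolution in expectation, so this is dilution, not confounding. A rule counting anyone who ever resolved would also give the 8-day arm more chances after randomisation (7 samples against 3). A net tilt towards the short course is therefore not assured.
- **Most response before randomisation.** This is not established. Clinical Response places substantial improvement at day 6, and the 3-5 days in the Background is microbiologic and straddles day 4.
- **Unused data.** The early values are used: on-treatment procalcitonin assesses response, may inform extension of therapy and feeds a sub-analysis. They are only not named as the randomisation baseline or as covariates.
- **Precision.** For continuous log procalcitonin, assumed correlations of 0.4 with the BAL-day value and 0.7 with the day-4 value give residual variances of 1 − 0.16 = 0.84 and 1 − 0.49 = 0.51, about 39% lower. The defined outcome is binary and the documents give no correlations, so no precision gain is claimed here.
- **Changing the reference.** A reader might conclude that the BAL-day reference is wrong. An 80% fall from an already treated day-4 value would be a different endpoint, and the 0.5 µg/L limb uses no reference value at all.

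**Conclusion.** The point holds as a gap in the outcome definition and in the covariate list. Procalcitonin resolution can be reached before allocation, and the plan does not say whether that counts. If it does, a 20-point deficit among patients unresolved at randomisation appears as 14, 10 or 6 points for shares of 30, 50 or 70% resolved by day 4. Those shares, the 20 points and the crediting rule are assumptions; the documents do not fix the size. Separately, the day-4 procalcitonin and CPIS_clinical values are collected but lie outside the pre-specified adjustment. Recurrence and the sample size based on it are not affected. The BAL-day reference can stay; the missing reading day is what needs correcting.

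**What to change.** 1. In Biomarker Response, keep both limbs of the resolution definition and the BAL-day reference, but state one common day after randomisation on which resolution is read. Days 5-7 are sampled in both arms. Day 7 is a reasonable choice, since day 5 is the randomisation morning itself. A patient resolved at randomisation then counts as a success only if still resolved on that day.
2. Add day-4 procalcitonin and day-4 CPIS_clinical to Baseline Variables.
3. In Data Analysis, pre-specify each as a covariate in the between-arm comparison of its own outcome, whatever its imbalance p-value. For CPIS this takes effect once a CPIS outcome is defined.

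**Cost.** The change is wording in three sections, with no new sample or visit. Resolution rates may look slightly less favourable. On day 7 the 8-day arm is still on treatment, so its post-treatment values (days 9-11) should be reported alongside. Some day-4 CPIS_clinical scores may be incomplete, because the protocol leaves unavailable components blank. The plan should also say how patients who have died or been discharged before the reading day are counted.
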